			20. Safety Reporting	Updated Safety Reporting	To align with data collection in the AUGS PFD Registry
07/AC	25 September 2017*	90702637 Rev/Ver AH	Title Page	Revised sponsor	To reflect BSC as sponsor
			Contact Information	Updated Clinical Contact	To reflect current BSC Clinical Project Manager
			Entire document	Changed reference to the “sponsor” to Boston Scientific	To clarify who the sponsor is
			2. Protocol Synopsis- Study Duration; 8.1. Scale and Duration; 11.4.7. Months 6, 12, 18, 24, 36 Visits	Deleted “per protocol” from subject description	To clarify the study population
			2. Protocol Synopsis- Planned Number of Subjects; 8.1. Scale and Duration	Deleted reference to Xenform subjects	To clarify which subjects will be shared from the PFD Registry
			10.1. Point of Enrollment	Revised study population description	To clarify the Intent-to-Treat and Per Protocol groups
			10.1. Point of Enrollment	Revised study timeline table	To update actual and expected dates for study milestones
			10.2. Withdrawal	Added sections on voluntary and involuntary withdrawal, lost to follow-up, death and documentation	To clarify early withdrawal categories
			11.1. Data Collection; 11.4.5. Follow-Up	Added definition of missed visit and ending 36 Month visit window	To clarify missed visit definition

Revision History

Revision Number	Release Date	Template Number and Version	Section	Change	Reason for Change
			12. Statistical Considerations	Various	To align with updated Statistical Analysis Plan
			11.3. Informed Consent; 13.2. Data Retention; 17.1. Statement of Compliance	Replaced reference to ICH-GCP with ISO14155:2011	To clarify which GCP standards were adhered to
			19.2.1. Mesh Exposure and Erosion Event Classification	Replaced physical exam with pelvic exam	To clarify exam type
			20. Informed Consent	Added Boston Scientific or designee for informed consent review	To clarify informed consent review process
			21. Safety Reporting	Revised section for AE definitions and reporting timelines	To clarify definitions and reporting timelines
08/AD	05 January 2018*	90702637 Rev/Ver AH	10.2.4. Subject Death; 11.6. Subject Death; 11.1. Data Collection; 21.6. Investigator Reporting Requirements	Revised collection of death information to include all events	To align with FDA Guidance on 522 Post-Market Surveillance
			12.1.1.3. Statistical Methods; 12.2.1. Analysis Sets	Added “per protocol” group to primary safety endpoint evaluation	To clarify evaluation of the primary safety endpoint
			12.3.5.4. Subjects with surgical intervention for recurrence or complications	Added section	To specify the analysis of adverse events by vaginal compartment after re-surgery
09/AE	20 March 2018	90702637 Rev/Ver AH	11.1. Data Collection; 11.4.5. Follow-Up	Increased window for follow-up visits to occur	To reduce number of late visits
			11.4.5. Follow-Up	Provide option for completion of home or phone follow-up visits; revised start day for visit window calculation	To improve collection of follow-up visit data and correct error in calculation of visit windows
			12.1.1.3. Statistical Methods	Added tipping point analysis	To clarify the sensitivity analyses to be performed

Revision History

Revision Number	Release Date	Template Number and Version	Section	Change	Reason for Change
			12.2.3. Propensity Score Methodology	Added definition of treatment arms	To clarify how logistic regression will be performed
			12.3.8. Interim Analysis	Added details of interim analysis of 12 month outcomes	Requested by FDA

** Not released to the study sites.*

2. Protocol Synopsis

Postmarket Study PS120081: A Prospective, Non-Randomized, Parallel Cohort, Multi-Center Study of Xenform vs. Native Tissue for the Treatment of Women with Anterior/Apical Pelvic Organ Prolapse	
Study Objective(s)	The purpose of this study is to compare transvaginal repair with a biologic graft to traditional native tissue repair in women surgically treated for anterior and/or apical pelvic organ prolapse. This study is being conducted in partnership with the American Urogynecologic Society (AUGS) under the Pelvic Floor Disorders Outcome Registry (PFD Registry).
Test Device	Xenform Soft Tissue Repair Matrix biologic graft (“Xenform”)
Control Device	Traditional native repair (sacrospinous ligament fixation or uterosacral ligament suspension and/or colporrhaphy)
Study Design	
Non-randomized, parallel cohort, multi-center study.
 
All procedures will be standardized for uniformity. Physicians will have to document a minimum of 10 procedures with either Xenform or a similar biologic graft or with native tissue repair prior to study participation in order to document competency and experience. Physician training, specialty, and site procedure location (such as private-practice, hospital, academic medical center, etc.) will be recorded.
 
Concomitant procedures including anterior and posterior vaginal wall repair, hysterectomy, and sling placement for stress urinary incontinence may be performed, per physician discretion. Sling placement can include a synthetic material, however a concomitant anterior or posterior repair cannot include a biologic graft or a synthetic implant. An anterior colporrhaphy may be required for cystocele repair, if clinically necessary. All concomitant procedures performed will be recorded.
 
Subjects who undergo a medical intervention (surgical or non-surgical) to treat recurrence, persistence of pelvic organ prolapse or a treatment complication will be followed to 36 months from the initial study procedure.

Planned Number of Subjects	Approximately 454 subjects enrolled (227 subjects per arm). Eligible control subjects meeting the study inclusion/exclusion criteria may be shared from the PFD Registry.

Postmarket Study PS120081: A Prospective, Non-Randomized, Parallel Cohort, Multi-Center Study of Xenform vs. Native Tissue for the Treatment of Women with Anterior/Apical Pelvic Organ Prolapse	
Planned Number of Investigational Sites / Countries	Up to 40 study centers
Primary Effectiveness Endpoint(s)	
The primary endpoint of the study is to achieve non-inferiority of transvaginal repair with Xenform over native tissue repair at 36 months as compared to baseline. Success will be based on a composite of objective and subjective measures, and subjects will be considered a surgical success if each of the three criteria is met:
 
 1. Subjective success is achieved if patient denies symptoms of vaginal bulging per PFDI-20 question 3, answering “no” or “yes” but “Not at all” bothersome (<2) 2. Anatomic success (in the operated compartment) 
 • Anterior Segment: Leading edge of prolapse is at or above the hymen or POP-Q point Ba \leq 0 • Apical Segment: The vaginal apex does not descend more than one-half into the vaginal canal (i.e. POP-Q point C < -1/2 TVL) for multi-compartment prolapse or POP-Q point C \leq 0 for prolapse of the apical compartment alone 3. No retreatment for POP: No additional surgical treatment for POP in the segment(s) of the vagina treated at the index surgery or no pessary use since index surgery (i.e., ‘treated segment’ refers to the target compartments in this study, which are the anterior and apical compartments)
Primary Safety Endpoint(s)	A co-primary endpoint of the study is to achieve non-inferiority of Xenform to native tissue repair for safety by comparing rates of serious device or serious procedure related complications between baseline and the 36 month time point. Serious injury is defined per 21 CFR 803.3, i.e., life threatening, results in permanent impairment of a body function or permanent damage to a body structure, or injury or illness that requires medical or surgical intervention to preclude impairment of a body function or permanent damage to a body structure.

Postmarket Study PS120081: A Prospective, Non-Randomized, Parallel Cohort, Multi-Center Study of Xenform vs. Native Tissue for the Treatment of Women with Anterior/Apical Pelvic Organ Prolapse	
Secondary Endpoints	
1. Incidence of Xenform erosion2. Incidence of Xenform exposure3. Incidence of de novo dyspareunia4. Improvement in subject specific outcomes at 36 months compared to Baseline (pelvic floor symptoms (PFDI-20), QOL (PFIQ-7), sexual functioning (PISQ-12), TOMUS pain scale)5. Assessment of subject’s level of improvement, measured by the Patient Global Impression of Improvement for Prolapse (PGI-I for Prolapse)6. Absence of re-intervention or re-surgery for recurrence or persistence of POP or mesh exposure/erosion7. Surgical success based on the following composite outcome:
a. Subjective success: patient denies symptoms of vaginal bulging per PFDI-20 question 3, answering “no” or “yes” but “Not at all” bothersome (<2)b. Anatomic success (in the operated compartment):
• Anterior Segment: No anterior prolapse at or beyond the hymen or POP-Q point Ba<0• Apical Segment: The vaginal apex does not descend more than one-half into the vaginal canal (i.e. POP-Q point C < 1/2 TVL) for multi-compartment prolapse or POP-Q point C < 0 for single compartment apical prolapsec. No retreatment for POP (treated segment): No additional surgical treatment for POP in the segment(s) of the vagina treated at the index surgery or no pessary use since index surgery (‘treated segment’ refers to the target compartments in this study, which are the anterior and apical compartments)8. Device or procedure-related incidence of the following: pelvic pain, infection, vaginal shortening, atypical vaginal discharge, neuromuscular problems, vaginal scarring, de novo vaginal bleeding, fistula formation and/or de novo voiding dysfunction

Postmarket Study PS120081: A Prospective, Non-Randomized, Parallel Cohort, Multi-Center Study of Xenform vs. Native Tissue for the Treatment of Women with Anterior/Apical Pelvic Organ Prolapse	
Method of Assigning Subjects to Treatment	This study is a prospective, non-randomized, parallel cohort, multi-center study. Approximately 454 subjects will be enrolled and will either receive transvaginal repair with Xenform (treatment) or a native tissue repair (control) procedure. Study centers will either participate to enroll only Xenform subjects or only native tissue subjects to reduce bias; or a combination of Xenform and native tissue subjects depending on subject population and per Boston Scientific’s discretion.
Follow-up Schedule	Study follow-up duration is for 3 years from primary study procedure: 
 • Screening/Enrollment Visit • Pre-procedure/Baseline Visit • Procedure and Discharge • Month 2 Visit • Month 6 Visit • Month 12 Visit • Month 18 Visit • Month 24 Visit • Month 36 Visit (Primary Endpoint and End of Study)
Study Duration	Approximately 3 years (36 months) from last subject enrolled.
Key Inclusion Criteria	
 1. Subject is female 2. Subject is ≥ 18 years of age 3. Subject has pelvic organ prolapse with the leading edge at or beyond the hymen. At or beyond the hymen is defined as POP-Q scores of $Ba \geq 0$ (for prolapse of the anterior compartment alone) or $C \geq 0$ (for prolapse of the apical compartment alone) or $C \geq -1/2$ TVL and $Ba \geq 0$ (for a multi-compartment prolapse that includes the anterior and apical compartments) 4. Subject reports of a bothersome bulge they can see or feel per PFDI-20, question 3 response of 2 or higher (i.e. responses of “somewhat”, “moderately” or “quite a bit”) 5. Subject or subject’s legally authorized representative must be willing to provide written informed consent 6. Subject is willing and able to comply with the follow-up regimen

Postmarket Study PS120081: A Prospective, Non-Randomized, Parallel Cohort, Multi-Center Study of Xenform vs. Native Tissue for the Treatment of Women with Anterior/Apical Pelvic Organ Prolapse	
Key Exclusion Criteria	
1. Subject is pregnant or intends to become pregnant during the study2. Subject has an active or chronic systemic infection including any gynecologic infection, untreated urinary tract infection (UTI) or tissue necrosis3. Subject has history of pelvic organ cancer (e.g. uterine, ovarian, bladder, colo-rectal or cervical)4. Subject has had prior or is currently undergoing radiation, laser therapy, or chemotherapy in the pelvic area5. Subject has taken systemic steroids (within the last month), or immunosuppressive or immunomodulatory treatment (within the last 3 months)6. Subject has systemic connective tissue disease (e.g. scleroderma, systemic lupus erythematosus (SLE), Marfan syndrome, Ehlers Danlos, collagenosis, polymyositis, polymyalgia rheumatica)7. Subject has chronic systemic pain that includes the pelvic area or chronic focal pain that involves the pelvis8. Subject has uncontrolled diabetes mellitus (DM)9. Subject has a known neurologic or medical condition affecting bladder function (e.g., multiple sclerosis, spinal cord injury or stroke with residual neurologic deficit)10. Subject is seeking obliterative vaginal surgery as treatment for pelvic organ prolapse (colpocleisis)11. Subject is not able to conform to the modified dorsal lithotomy position12. Subject is currently participating in or plans to participate in another device or drug study during this study13. Subject has a known sensitivity to any Xenform component14. Subject has had previous prolapse repair with mesh in the target compartment15. Subject is planning to undergo a concomitant prolapse repair with use of mesh in the non-target compartment

Postmarket Study PS120081: A Prospective, Non-Randomized, Parallel Cohort, Multi-Center Study of Xenform vs. Native Tissue for the Treatment of Women with Anterior/Apical Pelvic Organ Prolapse	
Statistical Methods	
Primary Statistical Hypothesis	
Transvaginal repair with Xenform will be non-inferior to traditional native tissue repair in effectiveness and non-inferior in safety.
 
Non-inferiority testing for effectiveness will be performed for the primary hypothesis.
 
Statistical testing will be performed to determine if composite endpoint of anatomic and symptomatic success rate in transvaginal biologic repair (treatment) group will be non-inferior to traditional native tissue repair (control) group. The null hypothesis is that the success rate in treatment group is less than or equal to the success rate in control group minus margin:
 $H_0: \pi_{treatment} - \pi_{control} \leq -\Delta$ 
The alternative hypothesis is:
 $H_a: \pi_{treatment} - \pi_{control} > -\Delta$ 
where $\pi_{treatment}$ and $\pi_{control}$ are the success rate in treatment group and control group respectively, and $\Delta > 0$ is defined as the non-inferiority margin.
 
Statistical testing will be performed to determine if the serious device-related or serious procedure-related complication rate of treatment group is non-inferior to the control group. The null hypothesis is that the complication rate in treatment group is greater than or equal to the rate in control group plus margin:
 $H_0: \pi_{treatment} - \pi_{control} \geq \Delta$ 
The alternative hypothesis is:
 $H_a: \pi_{treatment} - \pi_{control} < \Delta$ 
where $\pi_{treatment}$ and $\pi_{control}$ are the overall complication rate in treatment group and control group respectively, and $\Delta > 0$ is defined as the non-inferiority margin.

Statistical Test Method	
All statistical analyses will be performed by Boston Scientific per the Statistical Analysis Plan. All analyses will be done using SAS (version 8.0 or higher) statistical software. Subject summary tables and data listings will be provided for the data collected.

Postmarket Study PS120081: A Prospective, Non-Randomized, Parallel Cohort, Multi-Center Study of Xenform vs. Native Tissue for the Treatment of Women with Anterior/Apical Pelvic Organ Prolapse	
Sample Size Parameters	
The statistical power calculation is based on a non-inferiority assumption with a binary primary outcome. Success, based on a composite endpoint of anatomic and symptomatic success at 36 month is assumed to be 70%^{5-8, 16} for the native tissue arm. With type I error of 0.05 and type II error of 0.20 (power 80%), 362 subjects (181 subjects per arm) are needed to detect non-inferiority of transvaginal biologic to native tissue repair, using a margin of 12.0%.
 
To assess for safety, the overall complication rate (i.e., serious device-related or serious procedure-related adverse events) is anticipated to be approximately 14%.⁹ With type I error of 0.05 and type II error of 0.10 (power 90%), 308 subjects (154 subjects per arm) are needed to detect non-inferiority with a margin of 11.6%.
 
The rate of device or procedure related de novo dyspareunia is anticipated to be approximately 9%.¹⁷ With type I error of 0.05 and type II error of 0.20 (power 80%), 326 subjects (163 subjects per arm) are needed to detect non-inferiority with a margin of 7.9%.
 
The rate of device or procedure related AE incidence (pelvic pain, infection, vaginal shortening, atypical vaginal discharge, neuromuscular problems, vaginal scarring, de novo vaginal bleeding, fistula formation and/or de novo voiding dysfunction) is anticipated to be approximately 12%.¹⁵⁻¹⁸ With type I error of 0.05 and type II error of 0.20 (power 80%), 330 subjects (165 subjects per arm) are needed to detect non-inferiority with a margin of 8.9%.
 
To assess for office-based interventions for complications, the rate is anticipated to be approximately 2%.⁹ With type I error of 0.025 and type II error of 0.10 (power 90%), 330 subjects (165 subjects per arm) are needed to detect non-inferiority with a margin of 5%.
 
To assess for surgical intervention for complications, the rate is anticipated to be approximately 1%.⁹ With type I error of 0.025 and type II error of 0.10 (power 90%), 260 subjects (130 subjects per arm) are needed to detect non-inferiority with a margin of 4%.
 
Non-surgical subjects will not be enrolled in this study as all data on this cohort of subjects will be obtained from the AUGS PFD Registry and analyzed with data from this clinical study.
 
Assuming a 20% loss to follow-up rate, a total of 454 subjects (227 per study arm) will be enrolled to achieve the primary endpoint of success at 36 months.

3. Table of Contents

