10.1. Point of Enrollment

Subjects will be considered enrolled in the study once an incision is made in the vaginal wall. All enrolled subjects will have been consented and assigned to receive either the treatment or control procedure per site assignment. Per Boston Scientific's discretion, a site may be considered for participation in both the treatment and control procedure arms however each physician must be designated to one arm only. All enrolled subjects with a surgery initiated (i.e. incision in vagina) will be considered part of the Intent-to-Treat (ITT) population for the final study analysis. All ITT subjects who are treated with a study procedure and had no major protocol deviations will be considered part of the Per Protocol analysis.

The following study timeline (see Table 10.1-1) is based on milestones completed and the current follow-up visit cadence.

Table 10.1-1: Study Timeline

Study Milestones	Dates
Final FDA Approved Protocol	September 2013
First Site Initiated or Enrollment Ready	January 2014
Last Site Initiated or Enrollment Ready	December 2014
First Subject Enrolled	February 2014
Last Subject Enrolled	December 2016
Expected Date of Subject Follow-up Complete	December 2019
Expected Date of Final Database Lock/Study Completion	February 2020
Expected Date of Final Report Submission to FDA	June 2020

All efforts will be made by site staff to ensure minimal loss to follow-up of patients and will follow a site-specific loss to follow-up plan. The plan may include efforts such as telephone

follow-up, Investigator-patient counseling, visit reminder tools, patient stipends if permitted per site IRB, and/or other communication methods.

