12.1.2. Secondary Endpoints

Secondary endpoints will be to evaluate Xenform-related complications and subject reported outcomes as safety endpoints between baseline and 36 months:

1. Incidence of Xenform erosion
2. Incidence of Xenform exposure
3. Incidence of de novo dyspareunia
4. Improvement in subject specific outcomes at 36 months compared to Baseline (pelvic floor symptoms (PFDI-20), QOL (PFIQ-7), sexual functioning (PISQ-12), TOMUS pain scale)
5. Assessment of subject's level of improvement, measured by the Patient Global Impression of Improvement for Prolapse (PGI-I for Prolapse)
6. Absence of re-intervention or re-surgery for recurrence or persistence of POP or Xenform exposure/erosion
7. Surgical success based on the following composite outcome:
 - a. Subjective success: patient denies symptoms of vaginal bulging per PFDI-20 question 3, answering "no" or "yes" but "Not at all" bothersome (<2)
 - b. Anatomic success (in the operated compartment):
 - Anterior Segment: No anterior prolapse at or beyond the hymen or POP-Q point Ba<0
 - Apical Segment: The vaginal apex does not descend more than one-half into the vaginal canal (i.e. POP-Q point C < 1/2 TVL) for multi-compartment prolapse or POP-Q point C < 0 for single compartment apical prolapse.
 - c. No retreatment for POP (treated segment): No additional surgical treatment for POP in the segment(s) of the vagina treated at the index surgery or no

nessary use since index surgery ('treated segment' refers to the target compartments in this study, which are the anterior and apical compartments)

8. Device or procedure related incidence of the following: pelvic pain, infection, vaginal shortening, atypical vaginal discharge, neuromuscular problems, vaginal scarring, de novo vaginal bleeding, fistula formation and/or de novo voiding dysfunction

Definitions for the above listed adverse events are included in Section 21.2 (Definitions and Classifications). Rates of incidence for the adverse events will be stratified by primary or recurrent prolapse in both treatment groups.

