12.2. General Statistical Methods

12.2.1. Analysis Sets

The Intent-to-Treat (ITT) subject population includes all subjects who provide written informed consent to be enrolled into the study and have a surgery initiated (i.e. incision in vagina) regardless of their adherence with the entry criteria, regardless of treatment and withdrawal/protocol deviations.

The treated population includes all subjects who undergo a study surgical procedure. The subject is defined to have successfully completed the surgical procedure (i.e. prolapse repair successful) and discharged.

The Per Protocol (PP) population includes all subjects in the ITT Population who received the assigned treatment and had no major protocol deviations.

All primary and secondary endpoints will be analyzed on the ITT Population. The primary safety endpoint and non-safety endpoints will also be analyzed on the per-protocol population.

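### Section 12.2.1 leaves the secondary safety non-inferiority tests for dyspareunia and related adverse events on ITT alone, and the tests in 12.3.3 and 12.3.4 have no stated analysis set

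*Combined protocol and SAP*

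**What the plan says.** The operative text is Section 12.2.1 (Analysis Sets). Its general rule is "All primary and secondary endpoints will be analyzed on the ITT Population". ITT takes in every consented woman with a vaginal incision, "regardless of their adherence with the entry criteria, regardless of treatment and withdrawal/protocol deviations". One further sentence adds a second set: "The primary safety endpoint and non-safety endpoints will also be analyzed on the per-protocol population".

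The Per Protocol set in 12.2.1 is the ITT women "who received the assigned treatment and had no major protocol deviations". A third set is defined, "The treated population includes all subjects who undergo a study surgical procedure", but its next sentence ties it to a successful repair and discharge, and no analysis is assigned to it.

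The secondary tests affected are set out in 12.1.2.1 and 12.1.2.2 and in the synopsis. For related adverse events the assumed rate is 12%, and "330 subjects (165 subjects per arm) are needed to detect non-inferiority with a margin of 8.9" points. For de novo dyspareunia the assumed rate is 9%, with 163 per arm and a margin of 7.9 points. Section 12.1.2 introduces the whole secondary list with "Secondary endpoints will be to evaluate Xenform-related complications and subject reported outcomes as safety endpoints between baseline and 36 months".

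Sections 12.3.3 and 12.3.4 add non-inferiority tests for office-based interventions for complications (margin 5 points) and surgical interventions for complications (margin 4 points). Neither names an analysis set, and neither test is in the secondary endpoint list.

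Section 10.1 says that enrolled women are "assigned to receive either the treatment or control procedure per site assignment", that enrolment occurs at the vaginal incision, and that each physician works in one arm only.

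**The concern.** In a non-inferiority test of harm, a woman counted in an arm whose procedure she did not receive tends to shrink the difference between arms. A smaller difference makes non-inferiority easier to declare, so ITT should not be the only set for such a test. The plan evidently accepts this for the primary safety endpoint, since it adds Per Protocol there. It does not do so for dyspareunia and the adverse event composite, which lie closer to what a graft might cause.

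Xenform erosion and exposure raise a related problem. A woman with no graft cannot have either event, yet she stays in the ITT denominator, so the reported rate is too low by the share of such women.

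At stake is how much weight a secondary statement of non-inferior safety can bear, and whether the erosion and exposure rates describe women who actually have the graft.

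**Working it through.** **1. The plan's sample sizes.** Inputs: synopsis and 12.1.2.2. Formula, with equal true rates p and margin m: n per arm = (z₀.₉₅ + z₀.₈₀)² × 2p(1−p) / m², where (1.645 + 0.842)² = 6.183.
- Related adverse events: 6.183 × 2 × 0.12 × 0.88 / 0.089² = 164.8, so 165. The plan says 165.
- Dyspareunia: 6.183 × 2 × 0.09 × 0.91 / 0.079² = 162.3, so 163. The plan says 163.

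Both reproduce, with the 0.05 read as one-sided. The sample size is not in error.

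**2. Which set each test gets.**

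| Analysis | ITT | Per Protocol |
|---|---|---|
| Primary safety | yes | yes |
| Non-safety endpoints | yes, if primary or secondary | yes |
| Dyspareunia; related adverse events | yes | no |
| Office-based and surgical interventions (12.3.3, 12.3.4) | not stated | not stated |

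Sections 12.1.2.1 and 12.1.2.3 add no other set. Because 12.1.2 labels the whole secondary list as safety, it is unclear which secondary endpoints count as non-safety, but dyspareunia and the adverse event composite are safety endpoints on any reading.

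**3. Effect of women without a graft.** Let c be the share of Xenform-assigned women who receive no graft. The documents do not give c, so 2, 5 and 10% are assumptions. Further assumptions: the true difference by procedure received equals the margin, women without a graft carry the control risk, and all 227 per arm contribute.
- ITT Xenform rate: p_T = p_C + m(1−c)
- ITT difference: d = m(1−c)
- SE = √{[p_T(1−p_T) + p_C(1−p_C)] / 227}
- Probability of falsely declaring non-inferiority = Φ[(m − d)/SE − 1.645]

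Related adverse events, p_C = 0.12, m = 0.089:

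| c | p_T | d (points) | SE | (m−d)/SE | False non-inferiority |
|---|---|---|---|---|---|
| 0% | 0.2090 | 8.90 | 0.0346 | 0 | 5.0% |
| 2% | 0.2072 | 8.72 | 0.0345 | 0.052 | 5.6% |
| 5% | 0.2046 | 8.46 | 0.0344 | 0.129 | 6.5% |
| 10% | 0.2001 | 8.01 | 0.0342 | 0.260 | 8.3% |

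At 165 per arm the last three become 5.47, 6.25 and 7.74%. Dyspareunia at 227 per arm (p_C = 0.09, m = 0.079) gives 5.5, 6.5 and 8.2%.

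If the 12.3.3 and 12.3.4 tests were also run on ITT, which the plan does not say, the same formula with 1.96 in place of 1.645 gives 2.82, 3.37 and 4.51% for office-based interventions (p_C = 0.02, m = 0.05) and 2.81, 3.35 and 4.46% for surgical interventions (p_C = 0.01, m = 0.04), against 2.5%.

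**4. How far the direction depends on the risk of women without a graft.** If their risk is r, the ITT difference is d = m(1−c) + c(r − p_C). For related adverse events with c = 5%:
- r = 0.12 (control risk): d = 8.455 points, false non-inferiority 6.5%.
- r = 0.209 (same as with a graft): d = 8.90 points, 5.0%.
- r = 0.30 (an illustrative higher risk): d = 8.455 + 0.05 × 18 = 9.355 points, 3.8%.

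**5. Erosion and exposure.** With all events among women who have a graft, ITT rate = (1−c) × rate among those women. The relative understatement equals c, here 2 to 10%.

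**6. The two Per Protocol definitions.** Section 12.2.1 requires the assigned treatment. Section 10.1 asks only for a study procedure and no major deviation. Under 10.1, a Xenform-assigned woman given native tissue repair could remain in Per Protocol, and the added check would not remove the dilution.

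**The case against.** The strongest reply is that the design limits crossover. Each physician works in one arm, centres are by default confined to one arm (12.2.2), and a change of plan before incision never reaches ITT. At 2% without a graft the error rate moves by about half a percentage point, and nothing in the documents points to 10%. This stands. It makes the effect probably small, but does not supply the missing check.

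Second, the direction is conditional. ITT favours non-inferiority only if Xenform truly has more events and women without a graft carry roughly the control risk. A graft abandoned after incision may mark a difficult operation with a higher risk, and Per Protocol could then drop events from the Xenform arm. Step 4 of the working bears this out. It is a reason to show both sets rather than to rely on either.

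Third, serious device- or procedure-related complications already have ITT and Per Protocol analyses as the co-primary safety test. True; what remains concerns secondary tests.

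Fourth, analysis by assigned arm is nowhere written as a rule. It is inferred from the ITT and Per Protocol wording and from site assignment, though little other reading is open. The synopsis also refers to a Statistical Analysis Plan; if a separate one adds a set, the two texts need aligning.

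A reader might infer three stronger things, which the documents do not support. One is that all four non-inferiority tests are ITT-only; for 12.3.3 and 12.3.4 the set is simply not stated. Another is that dilution is known to occur, or occurs in both directions; no crossover figure is given in either direction. The third is that the sets must agree before any claim is made; the plan imposes no such rule even on its co-primary safety test.

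**Conclusion.** The point holds as a gap in the analysis sets. By the stated rule, the non-inferiority tests for de novo dyspareunia and related adverse events rest on ITT alone, while primary safety and non-safety endpoints also get Per Protocol. The 12.3.3 and 12.3.4 tests lack a stated set.

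The effect is of unknown and probably small size. With 2 to 10% of Xenform-assigned women without a graft and 227 per arm, the false non-inferiority rate is about 5.5 to 8.3% instead of 5% for these two tests. That range assumes a true difference at the margin, crossover in the Xenform arm only, and control risk in the women without a graft. The change is worth making because the plan already uses this check elsewhere; the figures do not show that a secondary conclusion would be wrong.

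**What to change.** 1. Replace the last sentence of 12.2.1 with wording to this effect: all primary and secondary endpoints, including the secondary safety endpoints, and the tests in 12.3.3 and 12.3.4, are analysed on ITT and also on Per Protocol.
2. Reconcile the Per Protocol definitions in 10.1 and 12.2.1 into one that requires the assigned procedure to have been received.
3. Report Xenform erosion and exposure with women in whom Xenform was placed as the denominator.
4. Optionally, add a supportive safety analysis by index procedure received, covering every woman with an incision whether or not the repair succeeded. The treated population as now worded does not serve this purpose.
5. Report the number of women in each arm who did not receive the assigned procedure, and any disagreement between sets. Agreement need not be a condition for a claim.

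Cost: items 1 to 3 and 5 need a few sentences and extra tables, with no new subjects. Item 4 costs more, because the propensity score must be re-estimated with procedure received as the treatment variable and the quintiles and balance checks redone. The downside is that a secondary non-inferiority statement becomes slightly harder to support.
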